4.3.2 Blinding

This is a double-blind clinical trial. For the entire clinical trial period, participating subjects, Investigators, study staff (subinvestigators, nurses, technicians, personnel involved in the administration of the investigational product, and other personnel) and testing laboratories will be blinded to the treatment group and the identity of solutions for infusion (test or placebo). Moreover, anyone from the sponsor (with the exception of the unblinded sponsor's clinical trial materials and drug safety staff) or CRO who will be involved in site monitoring will also be blinded regarding each subject's treatment group.

Unblinded personnel will be limited to:

- People responsible for creation of the randomization list who are independent of the study conduct.
- Site pharmacists or designees responsible for preparing and blinding the investigational products.
- The independent DMC for interim analysis.
- Unblinded sponsor's clinical trial materials personnel responsible for drug supply logistics

In order to address potential unblinding due to possible predictable side effects of the active product and product appearance, the following approaches will be employed:

- Pre-medication will be administered for subjects in all treatment arms and on both days of infusion to reduce the side effects of IVIG (see Section 7.2),
- All subjects will receive the same total dose volume (calculated to be equivalent to 2 g/kg Flebogamma® 5% DIF volume) for all treatments,
- Intravenous solution bags containing the investigational product solutions (test or placebo) will be covered with non-transparent sleeves,
- Connection between intravenous bag and intravenous line will be performed by unblinded staff to maintain the blind,
- Translucent or coloured lines will be used to maintain blind of the infusion system during the administration of the investigational product, and
- An independent assessor (neurologist or qualified personnel who will only have access to the efficacy data) will perform the evaluation of the efficacy endpoints. The independent assessor will not have any access to safety or AE data.

Except in the circumstances detailed in Section 5.6, the randomization code will not be broken until data entry is completed, validity of data is checked, all queries are resolved, each subject's populations for statistical analysis is agreed, and the database is locked.

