Abbreviations: EoTV: End of Treatment Visit; EV: Enrollment Visit; FU: Follow-up Visit; ICF: Informed Consent Form; FV/EDV: Final Visit/Early Discontinuation Visit; IV: Infusion Visit; SV: Screening Visit; w: Week.

- Events/activities should be performed in the order specified in Section 5 for each visit.
- b Time point for each visit is relative to EV/IV1. A ± 1-week window is allowed for all study visits after EV/IV1.
- c Assessments will be performed over at least 2 days within the specified visit window in the order specified in Section 5.
- d Physical examination by body systems.
- e Includes neurological examination, 12-lead ECG, and depression assessment using the Center for Epidemiologic Studies scale.
- f Borg scale is administered immediately before and immediately after the 2MWD and the 6MWD.
- Thromboembolic events risk monitoring will be performed before the beginning and after the completion of every infusion from IV1 (Week 0) to IV13 (Week 48).
- h Hemolysis detection will be performed before the beginning and after the completion of every infusion from IV1 (Week 0) to IV13 (Week 48).
- Each IV infusion is administered over 2 consecutive days for a total of 26 IV infusions [per IWRS IV1 Day 1, IV1 Day 2 up to IV13 Day 1, IV13 Day 2]. A window period of ± 1 week is allowed for any infusion after Infusion 1.

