4.5.2.15 Assessment of health-related quality of life

PPS may impact subject's HRQoL. This impact will be assessed by the generic tool Medical Outcomes Study 36-Item Short-Form Health Survey (SF-36) [63]. Data will be recorded at each specified visit without reference to previous answers.

SF-36 is a short-form health survey with 36 items that will be self-reported by the subjects. It yields an 8-scale profile of functional health and well-being scores as well as psychometrically-based physical and mental health summary measures. It is a generic measure that has proven useful in surveys of general and specific populations, and in differentiating health benefits produced by a wide range of different treatments. The 4-week recall form will be used (ANNEX 6). Scores calculation will be performed according to SF-36 user's manual and specified in the Statistical Analysis Plan (SAP).

SF-36 test will be administered by the principal investigator, subinvestigator, or designee study staff and reported by study individuals at the EV/IV1 (Week 0), IV4 (Week 12), IV7 (Week 24), IV10 (Week 36), EoTV (Week 52), FU3 (Week 64), and FV (Week 76). The principal investigator or subinvestigator will review (sign and date) the results of the assessment.

Sites affected by the COVID-19 pandemic can refer to ANNEX 18 for extraordinary contingency measures to be implemented.

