4.5.2.16 Assessment of pain

The VAS will be used to evaluate the pain level in a 24 hours period [64]. It consists of a 100 mm scale where 100 mm stands for the worst imaginable pain and zero stands for no pain (ANNEX 7).

VAS for pain will be administered by the principal investigator, subinvestigator, or other designee study staff and will be self-reported by study individuals at the EV/IV1 (Week 0), IV4 (Week 12), IV7 (Week 24), IV10 (Week 36), EoTV (Week 52), FU3 (Week 64), and FV (Week 76). The principal investigator or subinvestigator will review the results of the assessment.

Sites affected by the COVID-19 pandemic can refer to ANNEX 18 for extraordinary contingency measures to be implemented.

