4.5.2.24 Adverse events

AEs (includes suspected ADRs) occurring at any time between signature of the subject's informed consent form (ICF) and the last day of the subject's participation in the clinical trial will be reported and recorded on the appropriate subject's eCRF entry. Protocol Section 9.2.1 is specifically dedicated to AEs.

AEs occurring during the 2-day infusion period (*i.e.*, from the initiation of the investigational product infusion on the first day to the completion of the total dose of investigational product on the last day) and within 72 hours following the completion of the infusion of the total dose of investigational product on the last day, regardless of other factors that may impact a possible causal association with product administration, will be defined as infusional AEs (*i.e.*, an AE temporally associated with an infusion of the investigational product) and labeled treatment emergent adverse events (TEAEs).

AEs are to be assessed by the principal investigator or subinvestigator.

GRIFOLS

Clinically relevant changes in vital signs (T, RR, HR, SBP and DBP) during infusions of Flebogamma[®] 5% DIF or Normal Saline Solution will be reported as AEs. Clinical relevance will be based on the Investigator's judgment.

For AEs that occur during infusions, the infusion rate in effect at the time of onset of the AE, the time of onset of the AE and the time of AE change materially in intensity and/or resolve will be captured.

Sites affected by the COVID-19 pandemic can refer to ANNEX 18 for extraordinary contingency measures to be implemented.

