 - Subject vital signs (T, RR, HR, SBP and DBP) will be monitored (1) within 20 minutes before the beginning of each infusion; (2) every 30 ± 10 minutes during the first hour of each infusion; and (3) at 30 ± 10 minutes post-completion of each infusion.

Infusion Day 2:

- 6. Infusion and vital signs:
 - Infusion of investigational product.
 - Subject vital signs (T, RR, HR, SBP, and DBP) will be monitored (1) within 20 minutes before the beginning of each infusion; (2) every 30 ± 10 minutes during the first hour of each infusion; and (3) at 30 ± 10 minutes post-completion of each infusion.
- 7. Blood testing (blood sample collected at 30 ± 10 minutes post-completion of infusion).
 - D-dimer blood level for thromboembolic events risk assessment.
- 8. Wells score for thromboembolic events risk assessment (performed post-completion of infusion).
- Evaluation of clinical signs and symptoms of arterial and venous thromboembolic events (such as pain, dyspnea, discoloration—paleness or redness—in lower extremities) after completion of infusion.
- 10. Evaluation of clinical parameters of hemolysis including red/dark urine, jaundice, as well as other signs and symptoms of anemia (such as pallor, fatigue, or tachycardia) after completion of infusion.

Day 10:

11. Evaluation of clinical parameters of hemolysis including red/dark urine, jaundice, as well as other signs and symptoms of anemia (such as pallor, fatigue, or tachycardia) 10 days (±2 days) after the initiation of the infusion (Day 1) via telephone call.

Before next Infusion Visit:

- 12. Monitoring thromboembolic risk assessment (Section 4.5.2.5, ANNEX 13).
- 13. Hemolysis detection (Section 4.5.2.6, ANNEX 14).

Infusion Visit 4 (IV4) and Infusion Visit 10 (IV10)

Assessments and procedures planned to be done during the IV4 and IV10 will be performed over different days during a 1-week time window except for those assessments and procedures specifically indicated.

- 1. Physical assessment.
- 2. Weight.
- 3. Concomitant medication.
- 4. AEs.

*Procedures 5 through 8 must be performed on the same day and prior to the investigational product infusion in the following order:

- 5. Subject questionnaires: HRQoL (SF-36); Pain (VAS for pain).
- 6. Physical performance: 2MWD with assessment of perceived exertion/fatigue by Borg scale immediately before and immediately after 2MWD.

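### Pain VAS and SF-36 are not assured the independent-assessor safeguard of protocol 4.3.2 and are listed after the adverse-event review; arm-specific bias is plausible but not shown

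*Protocol*

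**What the plan says.** Protocol 4.3.2 lists measures against unblinding through predictable side effects and product appearance. One reads: "An independent assessor (neurologist or qualified personnel who will only have access to the efficacy data) will perform the evaluation of the efficacy endpoints". It continues: "The independent assessor will not have any access to safety or AE data". No exception is made for patient-reported endpoints.

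The procedure sections assign the three secondary endpoints as follows:

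- Pain VAS (4.5.2.16): "VAS for pain will be administered by the principal investigator, subinvestigator, or other designee study staff", with the subject reporting the score.
- SF-36 (4.5.2.15): "SF-36 test will be administered by the principal investigator, subinvestigator, or designee study staff", again reported by the subject.
- 6MWD (4.5.2.17): certified independent assessors.

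On AEs, 4.5.2.24 states: "AEs are to be assessed by the principal investigator or subinvestigator".

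On order, footnote a to Table 6 (4.5.1) states: "Events/activities should be performed in the order specified in Section 5 for each visit". Section 5 places the AE item before the questionnaires at every visit that has both. For IV4, IV10 and IV7, section 5.2 adds: "Procedures 5 through 8 must be performed on the same day and prior to the investigational product infusion in the following order". That sentence fixes the order from the questionnaires onward; AEs are item 4, just ahead of that block.

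**The concern.** The protocol treats side-effect unblinding as a real threat and chooses a specific protection, but the procedure sections do not carry that protection through to pain and SF-36. A subject may go through AEs with an investigator and then rate pain and quality of life on a form given by the same team.

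The possible routes to bias are clear. Sections 2.3 and 4.4.4.3 name headache, arthralgia, back pain, muscle cramps, fatigue and malaise among reactions to IVIG or infusional events, and these overlap with what a pain scale and SF-36 measure. The AE prompt suggested in 9.3.8 asks whether the subject feels different since the last visit, which is a global-change question placed ahead of the ratings. Analysing change from baseline would not remove an effect that differs by arm: EV precedes the first infusion, so AEs caused by treatment exist only afterwards.

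The testing order raises the stakes. Under protocol 10.1.2.2 and SAP 10.3, pain is tested first, SF-36 PCS second and 6MWD third, each only if the ones before it were rejected. A distortion in pain would therefore also decide whether the other two can be claimed.

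**Working it through.** The plan gives no figure for this point, so the main check sets the sections side by side.

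**Step 1. Who handles each secondary endpoint**

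| Endpoint | Place in sequence | Administered by | 4.3.2 safeguard assured? |
|---|---|---|---|
| Pain VAS | 1 | Investigator, subinvestigator or designee | No |
| SF-36 PCS | 2 | Investigator, subinvestigator or designee | No |
| 6MWD | 3 | Certified independent assessor | Yes |

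Two of three are not assured it. The word designee does not settle the matter. The synopsis counts certified independent assessors among study staff, but the staff list in 4.3.2 omits them, and 4.5.2.22 (FSS) names the certified independent assessor as an option separate from other designees. For VAS and SF-36 the safeguard is at most optional.

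**Step 2. Order within the visit (sections 5.2 and 5.3)**

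| Visit | AE item | Questionnaire item |
|---|---|---|
| EV | 4 | 5 |
| IV4, IV10 | 4 | 5 |
| IV7 | 4 | 5 |
| EoTV (Week 52) | 3 | 4 |
| FU3 | 3 | 5 (item 4 hands over the pedometer) |
| FV/EDV | 3 | 4 |

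The EoTV row matters most, because the secondary endpoints are read there. The AE-first order comes from this numbering together with footnote a. The sentence governing procedures 5 to 8 does not itself mention AEs.

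**Step 3. What the text leaves open**

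Footnote a says should, not must. Section 5 allows the procedures of these visits to be spread over different days in a one-week window, and the same-day rule begins with the questionnaires. So the same day and the same person are both possible, and neither is required.

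**Step 4. Sensitivity illustration (assumed inputs)**

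The documents give no SD for VAS change and no basis for a shift. Assumptions:

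- SD of change 20 mm, with a range of 15 to 25 mm.
- 66 evaluable subjects per arm, from the planned 99/3 = 33 in Stage 1 plus 66/2 = 33 in Stage 2.
- A simple two-group comparison at two-sided 5%.
- A true difference that has exactly 80% power.

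SE = 20 × √(2/66) = 3.48 mm. Difference for 80% power = 2.802 × 3.48 = 9.76 mm. Power after a shift b against active treatment = Φ((9.76 − b)/3.48 − 1.96).

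| Shift b | Power |
|---|---|
| 1 mm | 71% |
| 2 mm | 61% |
| 3 mm | 49% |

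Resetting the true difference to 80% power at each SD, a 2 mm shift gives 53% at SD 15 and 65% at SD 25. Across 1 to 3 mm and SD 15 to 25, power runs from 38% (SD 15, 3 mm) to 73% (SD 25, 1 mm). A shift in favour of active treatment would inflate the estimate by the same amount. This shows how sensitive the pain test is. It is not evidence that any shift occurs.

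**The case against.** The strongest reply is that the subject is the rater. Handing out a form is not evaluating an endpoint, and 4.3.2 can be read as covering tests that an assessor performs. Subjects and site staff are blinded, all arms receive pre-medication and equal volumes, and AEs are elicited with a non-leading question.

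Timing also helps the plan. Infusional AEs are those during an infusion or within 72 hours after it. Questionnaires at IV4, IV7 and IV10 precede that visit's infusion, EoTV falls nominally four weeks after IV13, and the VAS covers only 24 hours. For SF-36, with the four-week recall stated in 4.5.2.15, a genuine AE inside the recall window is legitimate content and not priming. Reordering would not erase what subjects and staff already know about AEs, since these are recorded at every visit.

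Most of this stands, and it limits how far the point can be taken. A reader might infer that the investigator who has just taken the AE history must then collect the pain score, or that the secondary results are biased by arm. The documents support neither inference: the roles allow a designee, the days may differ, and no arm-level AE rates are given. EV cannot carry arm-specific AE priming at all, because it precedes randomization and the first infusion.

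Two things remain. The wording of 4.3.2 does not match 4.5.2.15 and 4.5.2.16, and the listed order puts the AE review ahead of self-reports that are open to its influence.

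**Conclusion.** The point holds as an inconsistency and an avoidable risk. Pain VAS and SF-36 PCS, two of three secondary endpoints and the first two in the fixed sequence, are not assured the protection stated in 4.3.2 and may be rated after an AE review, including at Week 52. Differential priming by arm is a reasonable inference from the protocol's own concern about side effects, but it is not demonstrated.

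Its size cannot be estimated from the documents. The power figures rest wholly on an assumed SD, assumed shifts and the planned 66 per arm; SAP section 2 records early termination, so that number should not be taken as achieved. The primary endpoint's assessor safeguard is intact, since 4.5.2.14 gives the 2MWD to certified independent assessors. This is a cheap improvement to make and not a threat to the main result.

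**What to change.** - In sections 5.2 and 5.3, at IV4, IV7, IV10, EoTV, FU3 and FV/EDV, list the subject questionnaires before physical assessment, concomitant medication and AEs. Do the same at EV, for consistency only.
- In 4.5.2.15 and 4.5.2.16, have the certified independent assessor who runs the 2MWD hand out and collect SF-36 and VAS, so that both sections agree with 4.3.2. Section 5 already puts the questionnaires and the 2MWD on the same day, so no extra staff, visit or procedure is needed.

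The cost is a few minutes of assessor time per visit. There is one real drawback: for subjects already enrolled, baseline and later questionnaires would be taken in different orders. Apply the change to newly enrolled subjects only, or record the order used at each visit. Given the early termination, the practical step for this trial is to report who administered the forms and in what order as a limitation on the pain and SF-36 results, and to carry the corrected text into any later protocol.

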5.3 Follow-up period

Those individuals who have been enrolled will attend to their investigational site for follow-up visits after the treatment period. Different study assessments will be performed according to the follow-up visit number. A \pm 1-week window is allowed for all study visits in the follow-up period.

Sites affected by the COVID-19 pandemic can refer to ANNEX 18 for extraordinary contingency measures to be implemented.

Follow-up Visit 1 (FU1), Follow-Up Visit 2 (FU2), Follow-Up Visit 4 (FU4) and Follow-Up 5 (FU5)

The following assessments will be carried out at these visits by a phone call during a 1-week time window:

- 1. Assessment of symptoms and general well-being of the subject.
- 2. Concomitant medication.
- 3. AEs.
- 4. At FU5 (phone call), give instructions to subject about how and when to wear the pedometer.

Follow-Up Visit 3 (FU3)

Assessments and procedures planned to be done during the FU3 will be performed over different days during a 1-week time window:

- 1. Physical assessment.
- 2. Concomitant medication.
- AEs.
- 4. Provide subject with pedometer for walking activity in daily life assessment.

*Procedures 5 through 8 must be performed on the same day in the following order:

- 5. Subject questionnaires: HRQoL (SF-36); Pain (VAS for pain).
- 6. Physical performance: 2MWD with assessment of perceived exertion/fatigue by Borg scale immediately before and immediately after 2MWD.
- 7. Rest period (sitting on a chair for at least 30 minutes and until the subject feels fully recovered after completion of the 2MWD).
- 8. Endurance: 6MWD with assessment of perceived exertion/fatigue by Borg scale immediately before and immediately after 6MWD.
- 9. Blood testing:
 - Blood biochemistry and cell counts: CBC, including differential leukocyte count, creatinine, BUN, ALT, AST, ALP, TBL and GFR.

Final or Early Discontinuation Visit (FV/EDV)

Assessments and procedures planned to be done during the FV/EDV will be performed over different days during a 1-week time window:

- 1. Physical examination by body systems performed.
- 2. Concomitant medication.
- 3. AEs.

*Procedures 4 through 8 must be performed on the same day in the following order:

- 4. Subject questionnaires: Fatigue (FSS); HRQoL (SF-36); Pain (VAS for pain).
- 5. Record/upload number of steps from pedometer during 7 consecutive days prior to visit: Walking Activity in daily life.
- 6. Physical performance: 2MWD with assessment of perceived exertion/fatigue by Borg scale immediately before and immediately after 2MWD.
- 7. Rest period (sitting on a chair for at least 30 minutes and until the subject feels fully recovered after completion of the 2MWD).
- 8. Endurance: 6MWD with assessment of perceived exertion/fatigue by Borg scale immediately before and immediately after 6MWD.

- *Procedures 9 through 11 must be performed on the same day (on a different day after procedure 8) in the following order:

 9. Muscle strength: MMT.
- 10. Rest period (sitting on a chair for at least 30 minutes and until the subject feels fully recovered after completion of the MMT).
- 11. Muscle strength: QMT.
- 12. Blood testing:
 - Blood biochemistry and cell counts: CBC, including differential leukocyte count, creatinine, BUN, ALT, AST, ALP, TBL, and GFR.
 - Inflammatory cytokines: IL-1, IL-4, IL-6, IL-10, IL-13, IL-17, IL-23, TNF alpha, and IFN-gamma.
 - Retention blood sample for possible future biomarker testing.

5.4 Premature discontinuation of participating subjects

Study participation is strictly voluntary. Individuals have the right to withdraw from the study at any time for any reason. Likewise, the Investigator can withdraw an individual from the clinical trial at any time if it is deemed in the subject's best interest. The Investigator must document the reason(s) for withdrawal of each subject in the eCRF.

In the case an individual expresses his/her intention to withdraw from the study, but informed consent is still not withdrawn, subject will be asked if he/she is willing to perform a final visit (Early Discontinuation Visit) as soon as possible so that all study-related information can be recorded. Sponsor will have access to all data gathered on subjects prior to termination.

Subject withdrawal criteria and procedures are described in Section 6.3.

5.5 Accountability procedures for the investigational products

The investigational site pharmacist must keep accurate drug accountability records in IWRS per the Pharmacy Manual. These will include: (1) dates of receipt for investigational product (test or placebo); (2) when and how much investigational product (test or placebo) was dispensed; and (3) destruction of unused/undispensed investigational medicinal product.

In addition, reasons for deviations from the expected dispensing regimen must also be recorded.

All study medication will be reconciled at the completion of the clinical trial.

5.6 Maintenance of trial treatment randomization codes and procedures for breaking codes

In case of emergency, and when knowledge of the actual treatment becomes medically necessary to affect treatment options, the Investigator will be able to obtain details of the treatment assigned to an individual subject through the IWRS. A Medical Monitor will be informed immediately that blind has been broken regardless of whether emergency was

related to the study medication or not, but will not be informed of the treatment assignment. Every attempt should be made to maintain the blind throughout the study.

